### **Dose-Response at Weeks 4, 8 and 12**

A plot of the mean change from baseline in DAS28(CRP) score and 95% CI versus dose will be provided separately for each of Weeks 4, 8 and 12.

The dose-response relationship for the change from baseline in DAS28(CRP) score will be evaluated at Week 4, 8 and 12 using a three parameter  $E_{max}$  model of the form:

$$Y = E_0 + E_{max} * [Di / \{ ED_{50} + Di \}]$$

where  $E_0$  is the placebo effect,  $E_{max}$  is the maximum achievable effect above placebo,  $ED_{50}$  is the dose at half  $E_{max}$  and  $Di$  are doses =0, 22.5, 45, 90, 135 and 180 mg.  $Y$  is a measure of change from baseline in DAS28(CRP) continuous score.

If this Emax model is not applicable then additional models will be investigated, including a four parameter  $E_{max}$  model with a slope factor  $B > 0$ :

$$Y = E_0 + E_{max} * [Di^B / \{ ED_{50}^B + Di^B \}]$$

and the model with the expected response as a linear function of dose:

$$Y = E_0 + E_1 * Di$$

Each of the models will be fitted to the data and their fit compared using the Akaike information criteria (AIC), where the model with the lowest AIC will be the primary model for inference. The additional models will be considered secondary models, and will not be utilised unless issues arise with the residual checks on the primary model. Distributional assumptions will be assessed by examining plots of the residuals from the primary model.

The final model parameters for the dose-response will be summarised; a plot of the dose-response relationship will be provided. The chosen models might differ between Week 4, 8 and 12. SAS outputs of all secondary models will be shown.

## Posterior Probabilities at Week 12

In addition to assessing the dose response model for the DAS28(CRP) change from baseline data at Weeks 4, 8 and 12, the posterior distribution for the Week 12 change from baseline in DAS28(CRP) will be calculated.

This will be derived assuming the data follow a normal distribution with mean  $\mu_i$  and precision  $\tau_i$  (where  $i=0$  is the placebo group and  $i=1-5$  are the treatment groups) and non-informative prior distributions for  $\mu$  and  $\tau$ :

$$\mu_i \sim N(0, 10^{-2})$$

$$\tau_i \sim Ga(0.001, 0.001)$$

Given the small number of subjects expected with Week 12 data at the first interim analyses, alternative prior distributions for  $\tau$  may be investigated.

Markov-Chain-Monte-Carlo (MCMC) methods in SAS® will be used to derive the posterior distributions for each randomised treatment group and to also derive the distribution of the difference between each treatment group and the placebo group. From this difference distribution the posterior probability that the treatment difference between each active dose and placebo being  $> 1$  will be calculated.

Decision criteria for stopping the study after Interim Analysis 1 are specified in the DRC Statistical Guidance Document.

## DAS28 (CRP) remission rates at Week 24

The number and percentage of subjects achieving DAS28(CRP) remission ( $DAS28(CRP) < 2.6$ ) will be summarised for each randomised treatment group and visit. Fisher's exact test will be used to test for randomised treatment group differences at Week 24 in the proportion of subjects achieving remission for each GSK3196165 treatment group versus placebo.

## Predictive Probabilities at Week 24

The proportion of subjects with available DAS28(CRP) remission data at week 24 at the interim analysis will only be summarised using counts and proportions. This is because only a low number of subjects with week 24 data are expected at the week 12 interim analysis.

In addition, the predictive probability that the difference in DAS28(CRP) remission between each dose and placebo at the end of the study is  $> 15\%$  and  $> 25\%$ , given the results at the interim analysis and the prior information will be calculated using the procedure described below.

The following information will be available at the interim:

- $l_i$  = number of subjects that have reached week 24 in each randomised treatment group  $i$ ,  $i=0, \dots, 5$  ( $i=0$  being the placebo arm and  $i=1-5$  being the 5 treatment groups, with  $i=1$  being 22.5mg)
- $x_i$  = observed number of subjects in DAS28 remission at week 24 in each randomised treatment group  $i$ ,  $i=0, \dots, 5$  ( $i=0$  being the placebo arm and  $i=1-5$  being the 5 treatment groups, with  $i=1$  being 22.5mg)

Our prior Beta distribution on the remission rate in each randomised treatment group:  
 $\pi_i \sim \text{Beta}(\alpha_i^0, \beta_i^0)$

- Placebo:  $\alpha_0^0 = 9$ ,  $\beta_0^0 = 91$ , so the prior mean remission rate is 9%, and the 95th interval is (4%, 15%)
- Active group:  $\alpha_i^0 = 1$ ,  $\beta_i^0 = 1$ , equivalent to a uniform distribution (non informative). This will apply to all active groups ( $i=1$  to 5)

The algorithm is as follows:

1. Compute the interim posterior distribution of the remission rate  $\pi_i$  in each randomised treatment group:

$$\pi_i \sim \text{Beta}(\alpha_i = \alpha_i^0 + x_i, \beta_i = \beta_i^0 + l_i - x_i)$$

2. For each of the 6 treatment groups, a sample of the number of subjects with DAS28 remission post-interim is generated from the following predictive distribution (Beta-Binomial):

$$y_i \sim \text{beta-Binomial}(\text{sample} = m_i - l_i, \alpha_i, \beta_i)$$

Where  $m_i - l_i$  is the number of subjects remaining post-interim,  $\alpha_i$  and  $\beta_i$  are the parameters of the interim posterior distribution of the remission rate as calculated in (1).

10,000 replicates will be used per treatment group.

3. For each replicate, compute the distribution of the remission rate in each treatment group:

$$\pi_j \sim \text{Beta}(\alpha_i + y_i, \beta_i + m_i - y_i)$$

and therefore generate a sample of 10,000 simulations.

For each treatment group, we will obtain a matrix with 10000x10000, each column corresponding to the predictive distribution of  $\pi_i$  for each replicate from (2).

4. Calculate the posterior predictive distribution of the difference  $\pi_i - \pi_0$ , for  $i = 1, \dots, 5$   
For each of the 5 differences, we obtain again a matrix with 10000x10000, each column corresponding to the predictive distribution of the difference for each replicate from (2).
5. The posterior predictive probability  $p_j = P(15\% < \pi_j - \pi_0 < 25\%)$ ,  $j=1, \dots, 5$ , is calculated empirically by counting how many times the rule is met in the sample of the difference for each replicate. The median is used over the 10,000 replicates.

For sensitivity analysis purposes, other prior distributions for the placebo arm may be assessed based on emerging data on this endpoint, including assuming a non-informative prior.

The predictive probabilities to have an improvement of 25 percentage points over placebo will be used for the decision making, i.e. potentially dropping treatment arms or stop the study for futility. Decision criteria are specified in the DRC Statistical Guidance Document.

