**Table 4 Interim and Final Deliveries**

Analysis	Timing	Deliverable	Unblinded Team	Main Objective
Interim 1	90 subjects complete Week 4	PAREXEL: ADAM datasets and demography table (see Table 5 )  GSK: efficacy displays (see Table 5 ) and PK if required	Unblinded PAREXEL programmers, GSK lead and QC statistician, DRC	Evaluate whether to stop the study based on: • Dose response relationship at Week 4 (i.e., if all doses have $> -0.4$ point difference over placebo using the Week 4 dose response model estimates for change from baseline in DAS28(CRP)).
Interim 2	90 subjects complete Week 12	PAREXEL: ADAM datasets and demography table (see Table 5 )  GSK: efficacy displays (see Table 5 ) and PK if required	Unblinded PAREXEL programmers, GSK lead and QC statistician, DRC	Evaluate whether to stop the study based on: • Dose response relationship at Week 12 (i.e., if all doses have $> -1.0$ point difference over placebo using the Week 12 dose response model estimates for the change from baseline in DAS28(CRP)). • Dose response relationship and predictive probabilities (i.e., if at least one dose $\leq -1.0$ over placebo using the Week 12 dose response model estimates but the predictive probabilities of seeing a 25% difference at Week 24 in DAS28(CRP) remission is $<30\%$ ). Evaluate whether to drop a treatment arm based on: • An individual dose with $> -1.0$ point difference over placebo using the Week 12 dose response model estimates for change from

				baseline in DAS28(CRP).
Week 24	All subjects complete Week 24 visit	PAREXEL: Unblinded Week 24 displays.	PAREXEL lead and QC biostatisticians and programmers, GSK.	Unblinded primary/secondary analyses, safety and PK.
Final	All subjects complete the study (follow-up visit at Week 62)	PAREXEL: All unblinded displays, including exploratory endpoints, SDTM and ADAM datasets.	PAREXEL lead and QC biostatisticians and programmers, GSK.	Final reporting for Study 201755.

Unblinded interim analyses will be conducted when 90 subjects (i.e. on average 15 per arm) have completed 4 and 12 weeks of treatment. Efficacy analysis for the interim analyses will not be analysed by PAREXEL but by GSK. These interim analyses will be aligned with the unblinded safety review of the DRC where possible, see section [4.10.11](#).

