**Table 5 List of Outputs for Interim Analyses (IA)**

Endpoint	Output	IA1	IA2	Produced by
n/a	Summary of Demography Characteristics – Disease History	Y	Y	PAREXEL 
DAS28(CRP) change from baseline	Summary of the Change from Baseline in DAS28(CRP) at Each Visit	Y	Y	GSK
	Plot of Mean and 95% CI of Change from Baseline in DAS28(CRP) by Visit and Randomised Treatment Group (1 plot)	Y	Y	GSK
	Plot of Mean and 95% CI of Change from Baseline in DAS28(CRP) Across Doses at Weeks 4, 8 and 12 (3 plots)	Y	Y	GSK
	Mixed Model Repeated Measures Analysis (MMRM) of Change from Baseline in DAS28(CRP) Through Week 12	Y	Y	GSK
	Plot of Least Squares Means and 95% CI of Change from Baseline in DAS28(CRP) (from MMRM)	Y	Y	GSK
	Dose Response Modelling of Change from Baseline in DAS28(CRP) at Weeks 4, 8 and 12	Y	Y	GSK
	Plot of Dose Response Model at Weeks 4, 8 and 12	Y	Y	GSK
DAS28(CRP) remission	Posterior Probability of the Difference in the Change from Baseline over Placebo < -1.0 at Week 12 for Each Dose	Y	N	GSK
	Proportion of Subjects in DAS28(CRP) Remission at Week 24	N	Y	GSK
ACR response	Predictive Probability of the Difference Over Placebo in the Proportion of Subjects in DAS28(CRP) Remission at Week 24 being > 25%	N	Y	GSK
	Proportion of Subjects with an ACR20/50/70 Response at Each Visit	Y	Y	GSK

 Produced by the unblinded programming team.

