**Table 9 Assumed Change from Baseline in DAS28(CRP) Responses at 12 Weeks**

Treatment	Placebo	22.5 mg	45 mg	90 mg	135 mg	180 mg
DAS28(CRP) change from baseline	-1.0	-1.54	-1.83	-2.1	-2.24	-2.32
N	N=15	N=15	N=15	N=15	N=15	N=15

The assumed change from baseline in DAS28(CRP) of 1.0 points on the placebo arm is based on a review of studies in a DMARD-IR population.

It is expected that the shape of the dose response curve will be sigmoidal and the data for the DAS28(CRP) change from baseline was simulated assuming the following three parameter Emax model:

$$Y = E_0 + E_{\max} * [D_i / \{ ED_{50} + D_i \}]$$

[figure not shown]
Where  $E_0$  is the minimum dose effect,  $E_{\max}$  is the maximum achievable effect above  $E_0$ ,  $ED_{50}$  is the dose at half  $E_{\max}$  and  $D_i$  are the doses = 0, 22.5, 45, 90, 135 and 180 mg.  $Y$  is a measure of DAS28(CRP) change from baseline. In this case the  $E_0$  is the assumed effect with Dose=0 (placebo) which is -1.0 and the  $E_{\max}$  is taken as -1.65, the maximum achievable effect above placebo.

[Figure 1](#) shows the first 100 prediction curves (from 100000 simulations) and the overall median curve with the assumptions outlined above, illustrating the anticipated dose response curve with 15 subjects per arm. The black vertical intervals around each dose represent the change from baseline in DAS28(CRP) that are the 2.5 and 97.5 percentile values from all simulations.

The following table displays the proportion of simulations that are within a precision of 0.45 units in the change from baseline in DAS28(CRP) at each dose, with 15 subjects per arm. For the 135mg dose this is 98.9%.

**Table 10 Proportion of Simulations that are Within a Precision of 0.45 Units in the Change from Baseline in DAS28(CRP) at each Dose**

22.5 mg	45 mg	90 mg	135 mg	180 mg
90.4%	97.9%	98.8%	98.9%	95%

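### The SAP text defines the Week 12 posterior probability for a difference above +1 with no stated order of subtraction, while Table 5 defines the same Interim 1 output as below -1.0

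*SAP*

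**What the plan says.** Three places in the SAP bear on this output.

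- **Method text, 4.9.2.1, Posterior Probabilities at Week 12.** A normal model with non-informative priors is fitted to the Week 12 change from baseline in DAS28(CRP) in each arm. MCMC is then used to "derive the distribution of the difference between each treatment group and the placebo group". From that distribution the SAP takes "the posterior probability that the treatment difference between each active dose and placebo being" greater than 1. It gives no formula for the difference. The same text expects few subjects with Week 12 data at the first interim. It ends by placing the stopping criteria for Interim 1 in the DRC Statistical Guidance Document.
- **Table 5, outputs for the interims.** The output is "Posterior Probability of the Difference in the Change from Baseline over Placebo < -1.0 at Week 12 for Each Dose", marked Y for Interim 1 and N for Interim 2.
- **Table 4, interim decisions.** A reason to drop an arm at Interim 2 is "An individual dose with $> -1.0$ point difference over placebo using the Week 12 dose response model estimates" (the dollar signs are formula marks left by the PDF conversion). Reaching -1.0 or lower is favourable. The Interim 1 rule shown is that all doses lie above -0.4 on the Week 4 dose-response estimates.

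The planning section, 4.13.2, is on the same signed scale: E0 "is the assumed effect with Dose=0 (placebo) which is -1.0" and Emax "is taken as -1.65, the maximum achievable effect above placebo".

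**The concern.** The method text and Table 5 describe one quantity: same endpoint, same week, same comparison, same one-point margin. They disagree on its sign and on the direction of the inequality. A fall in DAS28(CRP) is improvement, so on the signed scale of Tables 4 and 5 a difference above +1 means that the active dose did worse than placebo by more than a point.

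At stake is an unblinded efficacy display that the DRC receives while it considers whether to stop the study. Programmed from the method text on the SAP's own convention, it would give low values to doses that work and the lowest value to the dose that works best.

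**Working it through.** **Inputs**

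- Planned Week 12 changes for placebo, 22.5, 45, 90, 135 and 180 mg: -1.0, -1.54, -1.83, -2.1, -2.24, -2.32 (SAP 4.13.2).
- Between-subject SD: 1 (SAP 4.13.2).
- Priors: mean N(0, 10^-2), read as precision 0.01 (variance 100) because the SAP calls it non-informative; precision Ga(0.001, 0.001) (SAP 4.9.2.1).
- Subjects per arm with Week 12 data at Interim 1: not stated. Assumed 3, 5 and 8. The average of 15 per arm with Week 12 data belongs to Interim 2 (Table 4).

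**Step 1: reproduce the planned means.** Y = -1.0 - 1.65 × D/(ED50 + D). ED50 is not in the readable text. Solving from the table gives 44.5 to 46.3. With ED50 = 45 the means are -1.55, -1.825, -2.10, -2.237 and -2.32, within 0.01 of the stated values. The SAP states no posterior probability, so there is no such figure to reproduce.

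**Step 2: differences, active minus placebo.** -0.54, -0.83, -1.10, -1.24, -1.32. All are negative, so benefit is negative on the SAP's scale.

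**Step 3: posterior.** Take sample means at the planned values, a sample SD of 1, and a flat approximation to the wide prior on the mean. Each arm mean then has a t posterior centred at the sample mean, with scale 1/√n and degrees of freedom 2 × [0.001 + (n - 1)/2], essentially n - 1. The difference of two such independent variables was integrated numerically.

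| Week 12 subjects per arm | Quantity | 22.5 mg | 45 mg | 90 mg | 135 mg | 180 mg |
|---|---|---|---|---|---|---|
| 3 | P(difference > 1) | 0.121 | 0.094 | 0.075 | 0.067 | 0.063 |
| 3 | P(difference < -1.0) | 0.34 | 0.44 | 0.54 | 0.59 | 0.61 |
| 5 | P(difference > 1) | 0.038 | 0.022 | 0.014 | 0.011 | 0.010 |
| 5 | P(difference < -1.0) | 0.27 | 0.41 | 0.55 | 0.63 | 0.67 |
| 8 | P(difference > 1) | 0.0075 | 0.0029 | 0.0013 | 0.0008 | 0.0007 |
| 8 | P(difference < -1.0) | 0.20 | 0.38 | 0.57 | 0.67 | 0.72 |

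In every > 1 row the values fall as dose rises; in every < -1.0 row they rise.

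**Step 4: sampling variation.** Averaged over 2,000 simulated data sets at 5 per arm, P(> 1) runs from 0.069 at 22.5 mg down to 0.018 at 180 mg. P(< -1.0) runs from 0.32 up to 0.63. The reversal persists on average, although a single small data set can lie far from these values.

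**The case against.** The strongest reply is that the method text never says active minus placebo. If the author meant placebo minus active, or the size of the reduction, then above 1 is the same event as Table 5's below -1.0. The SAP does sometimes write a reduction without its sign: 4.13.2 describes the placebo change as 1.0 points beside a table that shows -1.0. This stands in part. The text is ambiguous, so it is not proven that harm was meant. But that reading departs from Tables 4 and 5. It also departs from the order used for remission in the same section, where the difference is written as the active rate minus the placebo rate. Even if it was intended, the sign is left to the programmer.

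The second reply is that the SAP contains its own safeguards. Table 5 carries the right direction. The same Interim 1 package includes observed means, MMRM differences and dose-response fits, beside which a reversed probability would look odd. Table 4 also names both a lead and a QC statistician on the unblinded team. These make the error likely to be caught, but they do not make the two definitions agree.

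The third reply concerns size. A reader might take 15 per arm and a known SD of 1. At 180 mg the standard error is then √(2/15) = 0.365, P(< -1.0) = 0.81 and P(> 1) is about 1e-10, from which the reader would conclude that the text gives essentially zero for every effective dose. The documents do not support that for this output. It is produced at Interim 1 only, with fewer Week 12 subjects, and the SAP's model treats the precision as unknown. At 3 per arm the value reaches 0.12, which is low but not zero.

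**Conclusion.** The threshold in the method text is wrong as written on the SAP's own signed convention, and at best ambiguous. At the planned effects, with unknown variance and an assumed 3 to 8 Week 12 subjects per arm, it yields about 0.001 to 0.12 in place of about 0.20 to 0.72, with the dose order reversed. These figures rest on the assumed counts, on sample means equal to the planned values, and on reading the prior on the mean as wide.

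A reader might go further and infer that the study could be stopped for futility on this output. The documents do not show that. The only Interim 1 stopping rule in view uses the Week 4 model estimates against -0.4, and whether the DRC Statistical Guidance Document uses this probability cannot be seen. A wrong decision is a possible consequence, not a demonstrated one. The correction should be made because the display reaches the DRC unblinded and the two definitions cannot both be programmed as they stand.

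**What to change.** In SAP 4.9.2.1, Posterior Probabilities at Week 12, replace the threshold > 1 with < -1.0 and add that the difference is active minus placebo in change from baseline, as in Table 5. Then confirm that the DRC Statistical Guidance Document and the analysis program use the same direction. The cost is one line of SAP text and one check of each of those two items. The design, the data collected and the sample size are unaffected.

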### **9.4.2. Secondary Analyses**

The key secondary analysis of assessing dose response at 12 weeks will be based on the change from baseline in the DAS28(CRP) continuous score after 12 weeks of treatment. Primary inference will be based on the ITT population, as defined in Section 9.3.1 and the analysis will be performed using the OC dataset. Further sensitivity analyses using multiple imputation may be conducted if the rate of dropout is larger than expected (<10% to Week 12).

It is expected that the shape of the dose response curve will be sigmoidal and the data will be initially analyzed using a three parameter  $E_{max}$  model of the form:

$$Y = E_0 + E_{max} * [Di / \{ ED_{50} + Di \}]$$

where  $E_0$  is the minimum dose effect or placebo effect,  $E_{max}$  is the maximum achievable effect above placebo,  $ED_{50}$  is the dose at half  $E_{max}$  and  $Di$  are doses =0, 22.5, 45, 90, 135 and 180 mg.  $Y$  is a measure of DAS28(CRP) continuous score.

If this  $E_{max}$  model is not applicable then additional models will be investigated, including a four parameter  $E_{max}$  model and the model with the expected response as a linear function of dose. These models will be detailed in the reporting and analysis plan (RAP), along with further details of the analyses to be conducted. Each of the models will be fitted to the data and their fit compared using the Aikake information criteria (AIC), where the model with the lowest AIC will be the primary model for inference. The additional models will be considered secondary models, and will not be utilised unless issues arise with the residual checks on the primary model.

Distributional assumptions underlying this analysis will be assessed (further details will be included in the RAP).

All binary secondary endpoints will be analyzed using the same methods as for the primary endpoint. Continuous secondary endpoints, apart from the assessment of dose response, will be analyzed using a repeated measures model (MMRM). Further sensitivity analyses may be conducted using multiple imputation if the rates of dropout are high. Full details will be given in the RAP.

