#### 4.3.1 Analysis Datasets

For each of the efficacy evaluations of binary endpoints, subjects with missing efficacy data, early withdrawals, subjects who received more than 10 mg/day of prednisone equivalent oral corticosteroids, subjects with any new use of parenteral corticosteroids, more than one intra-articular corticosteroid injection within a 24 week period, or subjects who received rescue treatment will be imputed as non-responders and therefore treated as a failure (e.g. no DAS28(CRP) remission or no moderate/good EULAR response). Imputation rules for each case are described in section 4.5.2:

A dataset will be created with these imputation rules and will be referred to as the NRI dataset. The NRI dataset will be the primary dataset used for all binary efficacy endpoints. Imputed response for each binary endpoint will be presented by visit and subject in listings.

For the efficacy evaluations of continuous endpoints, results recorded for subjects who received rescue treatment or exceeded 10 mg/day prednisone equivalent oral corticosteroids, subjects with any new use of parenteral corticosteroids, more than one intra-articular corticosteroid injection within a 24 week period, or subjects who received rescue treatment will be set to missing at the same visits that were set to non-responder for the binary endpoints. This is a change from protocol section 9.3.2. A dataset will be created and will be referred to as the Set-to-Missing (STM) dataset.

For safety endpoints, no imputation for missing data will be done.

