## 4.5.2 Missing Data for Efficacy and Safety Endpoints

### 4.5.2.1 Missing Data for Efficacy Endpoints

Missing visit data for each efficacy endpoint will be handled as described in Sections 3.2 and 4.3.1. For each continuous endpoint, change from baseline will be missing at visits with missing post-baseline values or where data were imputed to missing.

For the binary endpoints, subjects with missing efficacy data, early withdrawals, subjects who exceed the allowed dose of corticosteroid, who received new parenteral corticosteroids or more than one intra-articular corticosteroid injection within a 24 week period, or subjects who received rescue treatment will be imputed as non-responders and therefore treated as a failure (e.g. no DAS28(CRP) remission or no moderate/good EULAR response).

For subjects who exceed the allowed dose of corticosteroid, who received new parenteral corticosteroids or more than one intra-articular corticosteroid injection within 24 weeks or subjects who received rescue treatment, continuous efficacy endpoints will be set to missing.

- Missing efficacy data: visits with missing data (due to a missed visit or missing component of a composite endpoint) should be set to treatment failure.
- Early withdrawals (including subjects that are withdrawn at Week 36 due to lack of EULAR response): only visits following the early withdrawal visit should be set to treatment failure.
- Prednisone equivalent >10 mg/day: the visit after a period (time from previous visit up to the day before the current visit) of average daily corticosteroid use exceeding 10 mg/day prednisone and all following visits should be set to treatment failure (continuous endpoints will be set to missing).
- Parenteral corticosteroids: all visits after a subject received any new parenteral corticosteroids (e.g. intravenous and intra-muscular) should be set to treatment failure (continuous endpoints will be set to missing).
- Intra-articular corticosteroids: all visits after the second intra-articular corticosteroid injection within a 24 week period should be set to treatment failure (continuous endpoints will be set to missing).
- Rescue: subjects who rescue to 180 mg dose at Week 14 or 26 should be set to treatment failure at that visit and all subsequent visits (continuous endpoints will be set to missing).

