#### **4.13.1 Primary Analysis**

The sample size for the primary analysis and hence the overall sample size for the study is based on detecting a 30% difference from placebo in the proportion of subjects in remission (DAS28 score <2.6) at Week 24 of the 52 week double-blind treatment period for each GSK3196165 dose.

Using a Fisher's exact test, a sample size of 35 subjects per arm will provide approximately 90% power to detect a difference of 30% in the proportion of subjects in remission between each GSK3196165 dose (33%) and placebo (3%) at the two-sided  $\alpha=0.05$  level at 24 weeks. The placebo rate of 3% is based on a literature review of current therapies presenting DAS28(CRP) remission results. No adjustments will be made to the sample size to account for the multiple doses in this Phase 2 study.

The least significant difference this sample size will detect is an approximate 17% difference from placebo.

The sample size will not be increased to account for dropouts and all dropouts within the treatment period will be classed as non-remitters for the primary analysis.

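### The Interim 2 remission rule in SAP 4.9.2.1 does not say that subjects who withdrew before Week 24 count in the interim denominator; read literally it leaves them out and is somewhat too lenient

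*SAP*

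**What the plan says.** SAP Table 4 lets the study stop at Interim 2 if at least one dose is at or below -1.0 against placebo on modelled Week 12 DAS28(CRP) change, but the predictive probability of a 25-point Week 24 remission difference is under 30%.

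Section 4.9.2.1 (Predictive Probabilities at Week 24) gives the algorithm:

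- l_i is the "number of subjects that have reached week 24 in each randomised treatment group".
- x_i is the "observed number of subjects in DAS28 remission at week 24 in each randomised treatment group".
- The same passage adds: "The proportion of subjects with available DAS28(CRP) remission data at week 24 at the interim analysis will only be summarised using counts and proportions".
- Step 2 draws remissions for m_i - l_i subjects, which "is the number of subjects remaining post-interim". It makes no exception for subjects whose outcome is already known.

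The endpoint behind the 25-point target is scored differently. SAP 4.13.1 states that "all dropouts within the treatment period will be classed as non-remitters for the primary analysis". SAP 4.3.1 states: "The NRI dataset will be the primary dataset used for all binary efficacy endpoints". SAP 4.5.2.1 adds that "subjects who rescue to 180 mg dose at Week 14 or 26 should be set to treatment failure at that visit and all subsequent visits".

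**The concern.** A subject who withdraws at Week 8 never reaches Week 24 and has no available remission result. Taken at its word, the algorithm never puts that subject in l_i. The subject stays among the m_i - l_i, and step 2 may draw a remission at the rate seen in those who completed. The endpoint has already fixed the result as failure. Leaving dropouts out of the denominator raises the apparent remission rate by a factor of 1/(1 - dropout).

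The remission criterion exists to catch a dose that moves mean DAS28(CRP) without raising remission. The SAP expects few subjects with Week 24 data at this look, so one uncounted dropout can decide the matter. What is at stake is a missed futility stop. The final analysis uses NRI in any case.

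**Working it through.** **Plan's own figures.** The SAP gives no pass or stop probabilities for this rule. Its neighbouring figures reproduce. Exact Fisher power for 33% against 3% with 35 per arm is 90.9% (stated: about 90%). The Beta(9,91) placebo prior has mean 9% and 2.5/97.5 percentiles of 4.2% and 15.3% (stated: 4%, 15%).

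**Inputs from the SAP.** Active prior Beta(1,1), placebo prior Beta(9,91), m = 35, median over replicates (step 5), pass at 30% or more.

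**Conventions.**
- Step 3 is taken as a proper update, adding m_i - l_i - y_i failures. As printed it adds m_i - y_i, which counts l_i failures too many and generally leaves pass rates the same or lower.
- The event is a difference above 25 points, as in Tables 4 and 5. Step 5 prints a range of 15% to 25%.

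**Assumptions.**
- True NRI remission is 9% in every arm (the placebo prior mean).
- Placebo has 0 remitters, with all due placebo subjects counted.
- Dropout by Week 24 is 10%. The documents give no Week 24 figure. Protocol 9.4.2 provides for sensitivity analyses "if the rate of dropout is larger than expected (<10% to Week 12").
- The number due at Week 24 per arm runs from 2 to 10.

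**Step 1: single outcomes.** Posterior Beta(1 + x, 1 + l - x) for the dose and Beta(9 + x0, 91 + l0 - x0) for placebo, followed by steps 2 to 5:

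- 1 remitter of 4: 0.38, continue
- 1 of 5: 0.18, stop
- 1 of 6: 0.085, stop

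One dropout left out of five due therefore turns a stop into a continue.

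**Step 2: false-pass rate per dose.** With all due counted, x ~ Bin(n, 0.09). With completers only, l = n - Bin(n, 0.10) and x ~ Bin(l, 0.09/0.90 = 0.10).

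Worked for n = 5, where 2 remitters are needed if l = 5, but only 1 if l is 1 to 4:

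- All counted: 1 - 0.91^5 - 5(0.09)(0.91^4) = 1 - 0.624 - 0.309 = 6.7%.
- Completers only, no dropout: 0.9^5 = 0.590, and P(x >= 2 | 5, 0.10) = 0.0815, giving 0.048.
- Completers only, some dropout: P(x >= 1) = 1 - 0.91^5 = 0.376, less the no-dropout part 0.590 × (1 - 0.590) = 0.242, giving 0.134.
- Sum: 0.048 + 0.134 = 18.2%.

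| Due per arm | Remitters needed if all counted | All due counted | Completers only |
|---|---|---|---|
| 2 | 1 | 17.2% | 18.2% |
| 3 | 1 | 24.6% | 24.7% |
| 4 | 1 | 31.4% | 31.4% |
| 5 | 2 | 6.7% | 18.2% |
| 6 | 2 | 9.5% | 12.8% |
| 7 | 2 | 12.5% | 13.3% |
| 8 | 3 | 2.9% | 9.5% |
| 9 | 3 | 4.0% | 6.7% |
| 10 | 3 | 5.4% | 6.2% |

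The average rise is about 3 points, and roughly 1.3 at 5% dropout and 4.8 at 15%. It is concentrated where the required number of remitters has just stepped up (5 and 8 due, then 6 and 9).

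**Step 3: the reading in which l_i already follows NRI.** A separate simulation took 15 per arm past Week 12, with E of them past Week 24, and assumed 5% withdrawal. It compared the SAP draw with one that models failures separately from remission among non-failures. Pass rates at E = 2/4/6/8:

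- DAS28(CRP) gain of 1.0, no remission gain (9% vs 9%, 8% escape on the dose): 17/30/10/3% against 18/16/9/4%.
- Effective dose (39% vs 9%, 8% escape): 65/84/75/66% against 64/71/72/70%.

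Apart from E = 4, where 1 of 4 sits just above the line, the differences are small and go both ways. The 8% escape rate follows from SAP 4.13.2: a change of -2.0 with SD 1 gives P(improvement <= 0.6) = Φ(-1.4) = 8%.

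**The case against.** **NRI already governs.** SAP 3.2.1 treats missing DAS28 as no remission, 4.3.1 applies NRI to binary efficacy evaluations, and the interim outputs use the ITT population. A programmer could sensibly put everyone past the Week 24 date in l_i. That is a fair reading, and under it the upward bias goes. But NRI says how to score a subject, not who belongs in l_i at a data cut, and the words *available* and *observed* point away from the sensible reading.

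**The definitions may be elsewhere.** The decision criteria are referred to the DRC Statistical Guidance Document, which is not supplied. This stands as a caveat. The SAP still prints the algorithm in full, so its inputs should be right there.

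**Escape adds little.** Escaped subjects stay in the study and reach Week 24, where NRI scores them as failures. Subjects on 180 mg cannot escape. A dose that has met -1.0 should have few escapers. All of this stands.

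**The effect is modest.** A reader might infer a much larger one by averaging over replicates: 1 of 5 then gives about 0.35 and 1 of 6 about 0.26, and the false-pass rate at 6 due rises from 9.5% to about 24%. The SAP does not support that, because step 5 takes the median, under which both outcomes stop.

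**Another driver is larger.** A uniform prior on the active arms (mean 50%) against an informative 9% placebo prior gives a predictive probability of 0.97 with no Week 24 data at all. This also stands. It is a separate matter and does not settle who is in l_i.

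**Conclusion.** The mismatch between the interim counts and the endpoint is in the text and should be corrected. On the literal reading, with withdrawn subjects outside l_i, the remission criterion is too lenient by about 3 points on average at 10% dropout. The clear rises are at 5 due (6.7% to 18%) and 8 due (2.9% to 9.5%). These figures rest on the assumed dropout, a 9% true rate, 0 placebo remitters, 35 per arm and the corrected step 3.

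The wider inference, that the rule passes no-benefit doses too often however l_i is read, is not supported. If l_i holds every subject past the Week 24 date under NRI, drawing already-failed subjects wastes information without a systematic upward bias, because those who have not failed are then drawn at too low a rate.

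Nor do the rates describe a wholly inert drug. They apply only after the -1.0 criterion. By simple pairwise comparison with 15 per arm and SD 1, the standard error is √(2/15) = 0.365, and an inert dose meets that criterion with probability Φ(-1/0.365) = Φ(-2.74), about 0.3%.

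**What to change.** In SAP 4.9.2.1, and identically in the DRC Statistical Guidance Document:

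1. Define l_i as all ITT subjects in arm i whose scheduled Week 24 date (Day 169 plus the visit window) falls on or before the data cut, whether or not they attended. Define x_i as those among them in remission under the NRI rules of 4.5.2.1. Remove *available* and *observed*.
2. In step 2, set subjects not yet due who have already withdrawn or escaped to no remission. Draw those still on randomised treatment at the rate among due subjects who were still on randomised treatment at the same stage. Draw subjects not yet enrolled at the overall NRI rate.
3. Do not simply add early failures to the posterior. Failure can be known by Week 14 but remission only at Week 24, so this biases the rule towards stopping. In the simulation above it cut the pass rate of the effective dose from 65/84/75/66% to 54/57/66/65% at E = 2/4/6/8.

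The cost is wording and a few lines of interim code, with no new data. Predictive probabilities become slightly less favourable.
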